**SYNOPSIS**

Protocol Title:	The TRANQUILITY Trial: A Multi-Center Randomized, Double-Masked, Parallel Design, Vehicle-Controlled Phase 2/3 Clinical Trial to Assess the Efficacy and Safety of 0.25% -Reproxalap Ophthalmic Solution Compared to Vehicle in Subjects with Dry Eye Disease
Protocol Number:	ADX-102-DED-019
Investigational Product:	0.25% Reproxalap Ophthalmic Solution (reproxalap)
Study Phase:	2/3
Primary Objective(s):	To evaluate the efficacy of reproxalap, as assessed by conjunctival redness, Schirmer's Test, and symptoms after dosing prior to and during exposure to the Controlled Adverse Environment® (CAE) in subjects with dry eye disease

**Overall Study Design:**

Structure:	Multi-center, double-masked, randomized parallel design trial
Duration:	An individual subject's participation is estimated to be approximately 16-32 days.
Controls:	Vehicle Ophthalmic Solution (vehicle)
Dosage/Dose Regimen:	
Test article (reproxalap or vehicle) will be dosed topically in both eyes.
 
Test article will be administered QID on Day 1 (Visit 2). On Day 2 (Visit 3), test article will be administered once within 10 minutes prior to the CAE entry, once 45 minutes after initiation of the CAE, and once at CAE® exit.

Summary of Visit Schedule:	
Three visits over the course of approximately 2 weeks:
 
 
• Visit 1 = Day -14 -16/+2, Screening
 

	
 
• Visit 2 = Day 1, Randomization/Baseline
 
• Visit 3 = Day 2 CAE® & Study Exit
 
 
Twenty subjects who meet the enrollment criteria will participate in an Initial Cohort. The Initial Cohort phase will be limited to Visit 1 (Screening), Visit 2 (Day 1), and Visit 3 (Day 2). Subjects will be randomized 1:1 to receive either reproxalap or vehicle. Results from the Initial Cohort phase will be analyzed to confirm endpoints, and statistical power for the remainder of the trial.

Measures Taken to Reduce Bias:	ADX-102-DED-019 is a randomized treatment assignment, double-masked trial.

**Study Population Characteristics:**

Number of Subjects:	
Twenty subjects are expected to be enrolled in the Initial Cohort of the trial.
 
Approximately 300 subjects are expected to be enrolled in the Main Cohort of the trial.

Condition/Disease:	Dry Eye Disease (DED)
Inclusion Criteria:	
Subjects must meet all of the following criteria:
 
 
1. 18 years of age (either gender and any race);
 
2. Ability to provide written informed consent and sign the Health Information Portability and Accountability Act (HIPAA) form;
 
3. Reported history of dry eye for at least 6 months prior to Visit 1;
 
4. Reported history of use or desire to use eye drops for dry eye symptoms within 6 months of Visit 1;
 
5. Corneal fluorescein staining sum [REDACTED] [REDACTED] [REDACTED] in at least one eye on the Ora Calibra Scale at Visit 1.
 
6. Response to the CAE at Visit 1, as defined by: 
 
a. [REDACTED]
 
[REDACTED]
 
[REDACTED]
 
 
 

	[REDACTED]
Exclusion Criteria:	
Subjects must not meet any of the following criteria:
 

1. Clinically significant slit lamp findings at Visit 1 [REDACTED] [REDACTED] [REDACTED] [REDACTED] [REDACTED] [REDACTED] [REDACTED]

2. Diagnosis of an ongoing ocular infection [REDACTED] or active ocular inflammation at Visit 1;

3. Contact lens use within 7 days of Visit 1 or anticipate using contact lenses during the trial;

4. Artificial tear eye drop use [REDACTED] [REDACTED]

5. Previous laser-assisted in situ keratomileusis (LASIK) surgery within the last 12 months;

6. [REDACTED] [REDACTED]

7. Systemic corticosteroid or other immunomodulator therapy [REDACTED] within 14 days of Visit 1 or any planned immunomodulatory therapy throughout the study period;

8. Planned ocular and/or lid surgeries over the study period or any ocular surgery within 6 months of Visit 1;

9. Temporary punctal plugs during the study that have not been stable within 30 days of Visit 1;

10. Use of and unwillingness to discontinue topical ophthalmic prescription (including medications

	
for glaucoma) or over-the-counter (OTC) solutions (not including artificial tears), gels, or scrubs for the duration of the trial (excluding medications allowed for the conduct of the trial);
 
11. Corrected visual acuity [REDACTED] [REDACTED] [REDACTED] [REDACTED] in both eyes at Visit 1;
 
12. Pregnancy, nursing, or planned pregnancy during the conduct of the trial;
 
13. Unwillingness to submit a urine pregnancy test at Visit 1 and Visit 3 (or early termination visit) if of childbearing potential. (Non-childbearing potential is defined as a woman who is permanently sterilized [e.g., has had a hysterectomy or tubal ligation], or is post-menopausal [without menses for 12 consecutive months]);
 
14. If of childbearing potential (female or male), unwillingness to use an acceptable means of birth control. (Acceptable methods of contraception include: hormonal – oral, implantable, injectable, or transdermal contraceptives; mechanical – spermicide in conjunction with a barrier such as a diaphragm or condom; intrauterine device [IUD]; or surgical sterilization of partner. For non-sexually active males or females, abstinence may be regarded as an adequate method of birth control; however, if the subject becomes sexually active during the study, he/she must agree to use adequate birth control as defined above for the remainder of the trial.);
 
15. Known allergy and/or sensitivity to the test article or its components;
 
16. A condition that the investigator feels may put the subject at significant risk, may confound the study results, or may interfere significantly with the subject's participation in the trial;

--	---

	
17. Current enrollment in an investigational drug or device study or have used an investigational drug or device within 30 days of Visit 1;
 
18. [REDACTED] [REDACTED]
 
19. Current use of any medication known to cause ocular drying that is not used on a stable dosing regimen for at least 30 days prior to Visit 1;
 
20. Inability or unwillingness to follow instructions, including participation in all study assessments and visits.

Study Formulations and Formulation Numbers:	0.25% Reproxalap Ophthalmic Solution
Evaluation Criteria:	
Primary Endpoint	

• Conjunctival redness assessed via digital photography over 90 minutes in CAE

Secondary Endpoints:	

• Visual analog scale eye dryness score [REDACTED] in CAE

• Ora Calibra® Ocular Discomfort Scale [REDACTED] in CAE

• Schirmer's Test [REDACTED] on Day 1

Exploratory Endpoints:	

• Visual analog scale [REDACTED] assessed over Days 1 and 2 [REDACTED]

• Ora Calibra® Ocular Discomfort Scale assessed over Days 1 and 2 (excluding CAE)

• Ocular Discomfort & 4-Symptom Questionnaire assessed over Days 1 and 2, and before and after CAE

• Ora Calibra® Conjunctival Allergen Challenge Ocular Itching Scale [REDACTED]

	

• Change in tear RASP levels [REDACTED]

• Conjunctival Redness [REDACTED]

• Conjunctival redness, Ora Calibra® Ocular Discomfort Scale, and visual analog scale dryness score [REDACTED]

Safety Endpoints:	

• Visual acuity

• Slit-lamp evaluation

• Adverse event query

• Intraocular Pressure (IOP)

• Dilated fundoscopy

General Statistical Methods and Types of Analyses:	
Statistical analyses will be detailed in the statistical analysis plan (SAP), which will dominate any statistical language herein. Any changes to protocol stated analyses will also be detailed in the SAP.	
Sample Size:	
Assuming [REDACTED] overall mean change from baseline in conjunctival redness (Ora Calibra® Scale) during the CAE at Day 2 between the two groups and a common standard deviation [REDACTED] [REDACTED] [REDACTED] [REDACTED]	
Multiplicity Considerations:	
[REDACTED] [REDACTED] [REDACTED] [REDACTED]	
Primary Efficacy Analyses:	
Overall mean change from baseline of conjunctival redness during the [REDACTED] will be assessed via mixed effect model for repeated measures [REDACTED] of change from baseline [REDACTED] with baseline score [REDACTED] [REDACTED]	
The primary endpoint will be assessed using the ITT population [REDACTED]	
Sensitivity analyses for the primary analyses will include the following:	

- [REDACTED]
- [REDACTED]
- [REDACTED]
- [REDACTED]
- [REDACTED]

## Secondary Efficacy Analyses:

For secondary efficacy endpoints during the [REDACTED] CAE, [REDACTED] will be assessed via [REDACTED] with baseline score as a covariate, nominal time, and treatment group, as fixed effects with correlated errors due to eye and nominal time point for eye level assessments. For subject level assessments [REDACTED], the model will have correlated errors due to nominal time point.

Overall mean change from baseline of Schirmer's Test [REDACTED] will be assessed [REDACTED] with baseline score as a covariate [REDACTED] time point [REDACTED] and treatment group as fixed effects with correlated errors due to eye and time point.

## Exploratory Efficacy Analyses:

Term	Percentage
GMOs	95
Organic	92
Natural	90
Artificial	10
GMOs	95
Organic	92
Natural	90
Artificial	10
GMOs	95
Organic	92
Natural	90
Artificial	10
GMOs	95
Organic	92
Natural	90
Artificial	10

Primary analyses of exploratory efficacy endpoints will utilize the ITT population with observed data only.

All efficacy analyses conducted on the ITT population will be conducted using the Initial Cohort population only with observed data.

Safety Analyses:

**Summary of Known and Potential Risks and Benefits to Human Subjects:**

Refer to Investigator's Brochure.

## List of Abbreviations

AE	adverse event
CAE	Controlled Adverse Environment®
CFR	Code of Federal Regulations
DED	dry eye disease
DES	dry eye syndrome
DHHS	Department of Health and Human Services
ETDRS	Early Treatment of Diabetic Retinopathy Study
FDA	Food and Drug Administration
GCP	Good Clinical Practice
HIPAA	Health Information Portability and Accountability Act
ICF	informed consent form
ICH	International Council for Harmonisation
IEC	Independent Ethics Committee
IRB	institutional/independent review board
LogMAR	logarithm of the minimum angle of resolution
MAR	Missing at random
MNAR	Missing not at random
Ora	Ophthalmic Research Associates, Inc.
OTC	over the counter
RASP	reactive aldehyde species
SAE	serious adverse event
µL	microliter
VA	visual acuity
VAS	Visual analog scale

## 1 INTRODUCTION

A series of ten horizontal black bars of varying heights, creating a stepped or staircase pattern. The bars are evenly spaced and extend across the width of the frame. The heights of the bars increase from left to right, starting with a very low bar on the far left and ending with a very high bar on the far right.

A horizontal row of four solid black rectangular bars, evenly spaced and aligned horizontally.

A solid black rectangular bar is positioned at the bottom of the slide, spanning most of the width. It is likely a placeholder for a logo or a decorative element.

A series of horizontal black bars of varying heights, creating a stepped or staircase pattern. The bars are arranged in a descending sequence from left to right, with the tallest bar on the far left and the shortest bar on the far right. The bars are set against a white background.

## **2 STUDY OBJECTIVES**

To evaluate the efficacy of reproxalap, as assessed by conjunctival redness, Schirmer's Test, and symptoms after dosing prior to and during exposure to the Controlled Adverse Environment® (CAE) in subjects with dry eye disease

## **3 CLINICAL HYPOTHESES**

The clinical hypothesis is that reproxalap is more effective than vehicle in reducing the signs and symptoms of DED.

## 4 OVERALL STUDY DESIGN

ADX-102-DED-019 is a Phase 2/3, multi-center, randomized, double-masked, parallel design, vehicle-controlled trial designed to evaluate the efficacy and safety of 0.25% Reproxalap Ophthalmic Solution compared to vehicle in subjects with dry eye disease. Approximately twenty subjects will be enrolled in the Initial Cohort, and approximately 300 subjects will be enrolled in the Main Cohort. Male and female subjects at least 18 years of age with a subject-reported history of dry eye disease in both eyes and meeting all other eligibility criteria will be randomized to receive reproxalap or vehicle in a 1:1 ratio (approximately 150 subjects in each treatment group).

Visit 1  (Day -14 -16/+ 2):  Screening
	
 
• Informed Consent
 
• Demographics, Medical/Medication & Ocular History
 
• Urine Pregnancy Testing (as needed)
 
• Symptom Questionnaires, Ocular Dryness VAS, Visual Acuity
 
• Ora Calibra® Conjunctival Allergen Challenge Ocular Itching Scale
 
• Slit Lamp Exam with Conjunctival Redness assessment
 
• In-Office vehicle dose [REDACTED]
 
• CAE exposure [REDACTED] with Ocular Dryness VAS, Ora Calibra® Ocular Discomfort Scale, and Conjunctival Redness Assessment
 
• Slit Lamp Exam with Conjunctival Redness assessment
 
• Ora Calibra® Corneal and Conjunctival Staining Scale
 
• Schirmer's Test
 
• IOP and Dilated Fundoscopy
 

Visit 2  (Day 1):  Randomization/Baseline
	
 
• Medical/Medication Update: AE Query
 
• Visual Acuity
 
• Slit Lamp Exam
 
• Symptom Questionnaires at specified time points
 
• Conjunctival Redness at specified time points
 
• In-Office Doses (QID)
 
• Tear Collection & Schirmer's Test at specified time points
 

Visit 3  (Day 2):  CAE
	
 
• Medical/Medication Update: AE Query
 
• Urine Pregnancy Testing (as needed)
 
• Visual Acuity, Slit Lamp Exam
 
• Symptom Questionnaires
 
• Conjunctival Redness at specified time points
 
• In-Office Doses [REDACTED]
 

	

• CAE exposure [REDACTED] with Ocular Dryness VAS, and Ora Calibra® Ocular Discomfort Scale, and Conjunctival Redness Assessments

• Tear Collection at specified time points

• IOP and Dilated Fundoscopy

• Study Exit

--	--

## 5 STUDY POPULATION

### 5.1 Number of Subjects (approximate)

Approximately 40 subjects will be screened in the Initial Cohort to enroll 20 subjects at one site. An additional 600 subjects will be screened in the Main Cohort to enroll approximately 300 subjects across approximately 8 sites.

### 5.2 Study Population Characteristics

All subjects must be at least 18 years of age, be of either sex and of any race, have a subject-reported history of dry eye disease, and meet all of the inclusion criteria and none of the exclusion criteria.

### 5.3 Inclusion Criteria

**Each subject must meet each of the following criteria:**

1. 18 years of age (either gender and any race);
2. Ability to provide written informed consent and sign the Health Information Portability and Accountability Act (HIPAA) form;
3. Reported history of dry eye for at least 6 months prior to Visit 1;
4. Reported history of use or desire to use eye drops for dry eye symptoms within 6 months of Visit 1;
5. Corneal fluorescein staining sum [REDACTED] in at least one eye on the Ora Calibra Scale at Visit 1.
6. Response to the CAE at Visit 1, as defined by:
  - a. A [REDACTED] in the visual analog scale eye dryness score [REDACTED] in at least one eye during at least two consecutive time points in CAE and;
  - b. A [REDACTED] in conjunctival redness score measured via digital photography in at least one eye during at least two consecutive time points in CAE.

Eye does not need to be the same eye as inclusion 5 or 6a.

## 5.4 Exclusion Criteria

**Each subject may not meet any of the following criteria:**

1. Clinically significant slit lamp findings at Visit 1 that may include active blepharitis, meibomian gland dysfunction (MGD), lid margin inflammation, or active ocular allergies that require therapeutic treatment, and/or in the opinion of the investigator may interfere with study parameters;
2. Diagnosis of an ongoing ocular infection [REDACTED] or active ocular inflammation at Visit 1;
3. Contact lens use within 7 days of Visit 1 or anticipate using contact lenses during the trial;
4. Artificial tear eye drop use within 2 hours of Visit 1 or within 24 hours of Visit 2 (drops cannot be used on the day of Visit 2 or Visit 3);
5. Previous laser-assisted *in situ* keratomileusis (LASIK) surgery within the last 12 months;
6. Cyclosporine 0.05% or 0.09% or lifitegrast 5.0% ophthalmic solution use within 90 days of Visit 1;
7. Systemic corticosteroid therapy or other immunomodulator (not including inhaled corticosteroids) within 14 days of Visit 1 or anticipate such therapy throughout the study period;
8. Planned ocular and/or lid surgeries over the study period or any ocular surgery within 6 months of Visit 1;
9. Temporary punctal plugs during the study that have not been stable within 30 days of Visit 1;
10. Use of and unwillingness to discontinue topical ophthalmic prescription (including medications for glaucoma) or over-the-counter (OTC) solutions (not including artificial tears), gels or scrubs for the duration of the trial (excluding medications allowed for the conduct of the trial);
11. Corrected visual acuity greater than or equal to logarithm of the minimum angle of resolution [REDACTED] at Visit 1;
12. Pregnancy, nursing, or planned pregnancy during the conduct of the trial;
13. Unwillingness to submit a urine pregnancy test at Visit 1 and Visit 3 (or early termination visit) if of childbearing potential. (Nonchildbearing potential is

defined as a woman who is permanently sterilized [e.g., has had a hysterectomy or tubal ligation], or is post-menopausal [without menses for 12 consecutive months]);

14. If of childbearing potential (female or male), unwillingness to use an acceptable means of birth control. (Acceptable methods of contraception include: hormonal – oral, implantable, injectable, or transdermal contraceptives; mechanical – spermicide in conjunction with a barrier such as a diaphragm or condom; intrauterine device [IUD]; or surgical sterilization of partner. For non-sexually active males or females, abstinence may be regarded as an adequate method of birth control; however, if the subject becomes sexually active during the study, he/she must agree to use adequate birth control as defined above for the remainder of the trial.);
15. Known allergy and/or sensitivity to the test article or its components;
16. A condition that the investigator feels may put the subject at significant risk, may confound the study results, or may interfere significantly with the subject's participation in the trial;
17. Current enrollment in an investigational drug or device study or have used an investigational drug or device within 30 days of Visit 1;
18. Use of [REDACTED] solution in the past year;
19. Current use of any medication known to cause ocular drying that is not used on a stable dosing regimen for at least 30 days prior to Visit 1;
20. Inability or unwillingness to follow instructions, including participation in all study assessments and visits.

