### 7.1.4 Instructions for Dispensation, Use, and Administration

- At Visit 1, qualified subjects will be assigned a vehicle kit. Subjects will use two vials from the kit for Visit 1 in-office doses. After use, vials will be placed into a zip locked bag labeled with subject's initials and screening number for accountability.
- At Visit 2, qualified subjects will be randomized and will be assigned a single kit of 14 pouch supply of Reproxalap Ophthalmic Solution 0.25% or Vehicle. Subjects will be dosed in office four times (QID) by trained site staff.
- At Visit 3, subjects will be dosed three times in-office from the same kit by trained site staff.

[REDACTED]

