## 8.3 **Examination Procedures**

### 8.3.1 Procedures to be Performed at the Study Visit with Regard to Study Objective(s)

#### **Visit 1 (Day -14 -16/+2, Screening)**

- Informed Consent and HIPAA
- Demographics [REDACTED]
- Medical/Medication & Ocular History
- Urine Pregnancy Test (as needed)
- Symptom Questionnaires:
  - Ocular Discomfort & 4-Symptom Questionnaire
  - Ora Calibra® Ocular Discomfort Scale
  - Ocular Dryness Visual Analog Scale
  - Ora Calibra® Conjunctival Allergen Challenge Ocular Itching Scale
- Visual Acuity (ETDRS)
- Slit Lamp Biomicroscopy with Conjunctival Redness assessment
- Fluorescein Staining using the Ora Calibra® Corneal and Conjunctival Staining Scale
- Inclusion/Exclusion Criteria Review
- In-Office Vehicle Instillation by trained site staff [REDACTED]  
[REDACTED]
- CAE Exposure [REDACTED]  
with:
  - Ocular Dryness Visual Analog Scale [REDACTED]
  - Ora Calibra® Ocular Discomfort Scale [REDACTED]
  - Conjunctival Redness Photography [REDACTED]  
[REDACTED]
- Slit Lamp Biomicroscopy with Conjunctival Redness assessment
- Schirmer's Test
- Intraocular Pressure

- Dilated Exam
- Schedule for Visit 2

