### Visit 2 (Day 1, Baseline and In-Office Dosing)

- Medical/Medication Update
- Adverse Event Query
- Visual Acuity (ETDRS)
- Slit Lamp Biomicroscopy
- Symptom Questionnaires
  - Ocular Discomfort & 4-Symptom Questionnaire
  - Ora Calibra® Ocular Discomfort Scale
  - Ocular Dryness Visual Analog Scale
  - Ora Calibra® Conjunctival Allergen Challenge Ocular Itching Scale
- Conjunctival Redness Photography
- Inclusion/Exclusion Criteria Review
- Randomization/Enrollment
- Pre-dose #1 [REDACTED]
- In-Office Dose #1 [REDACTED]
- Post-dose #1 [REDACTED]  
[REDACTED]
- Pre-dose #2 [REDACTED]
- In-Office Dose #2 [REDACTED]
- Post-dose #2 [REDACTED]  
[REDACTED]
- In-Office Dose #3
- Conjunctival Redness Photography [REDACTED]  
[REDACTED]
- Symptom Questionnaires started within [REDACTED]  
[REDACTED]
  - Ocular Discomfort & 4-Symptom Questionnaire
  - Ocular Discomfort
  - Ocular Dryness Visual Analog Scale
  - Ora Calibra® Conjunctival Allergen Challenge Ocular Itching Scale

*Wait 30 minutes between doses*

- Pre-dose #4 Schirmer's Test [REDACTED]
  - Weigh Schirmer's Test strip before and after use
- In-Office Dose #4
- Post-dose #4 Schirmer's Test [REDACTED]

- Weigh Schirmer's Test strip before and after use
- Schedule for Visit 3

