### Visit 3 (Day 2, CAE®)

- Medical/Medication Update
- Adverse Event Query
- Urine Pregnancy Test (as needed)
- Visual Acuity (ETDRS)
- Slit Lamp Biomicroscopy
- Conjunctival Redness Photography
- Symptom Questionnaires:
  - Ocular Discomfort & 4-Symptom Questionnaire
  - Ora Calibra® Ocular Discomfort Scale
  - Ocular Dryness Visual Analog Scale
  - Ora Calibra® Conjunctival Allergen Challenge Ocular Itching Scale
- Pre-dose #1 [REDACTED]
- In-Office Dose #1 [REDACTED]
- CAE Exposure [REDACTED] with:
  - Ocular Dryness Visual Analog Scale [REDACTED]
  - Conjunctival Redness [REDACTED]  
[REDACTED]  
[REDACTED]
  - Ora Calibra® Ocular Discomfort Scale [REDACTED]
- In-Office [REDACTED]  
[REDACTED]
- Post-CAE exit [REDACTED]
- In-Office Dose #3 [REDACTED]
- Symptom Questionnaires [REDACTED]  
[REDACTED]
  - Ocular Discomfort & 4-Symptom Questionnaire
  - Ocular Discomfort
  - Ocular Dryness Visual Analog Scale
  - Ora Calibra® Conjunctival Allergen Challenge Ocular Itching Scale
- Post-dose #3 [REDACTED]
- Slit Lamp Biomicroscopy
- Intraocular Pressure
- Dilated Exam
- Study Exit

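### No urine pregnancy test is scheduled before randomization at Visit 2: the last result is 12 to 30 days old at the first randomized dose, and four of the seven doses precede the next test

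*Protocol*

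**What the plan says.** Pregnancy is an exclusion (Protocol 5.4, criterion 12). Criterion 13, in the synopsis and in 5.4, sets the test visits by excluding subjects for "Unwillingness to submit a urine pregnancy test at Visit 1 and Visit 3 (or early termination visit) if of childbearing potential". The table in Protocol Section 4 lists the test under Visits 1 and 3, and so do the procedure lists in 8.3.1. Neither Visit 2 list contains it.

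Visit 2 is the day of randomization. Its list in 8.3.1 has a medical and medication update and, directly before randomization, an item headed "Inclusion/Exclusion Criteria Review". Criterion 14 adds a contraception condition: "If of childbearing potential (female or male), unwillingness to use an acceptable means of birth control".

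On dosing, Protocol 7.1.4 says of Visit 2: "Subjects will be dosed in office four times (QID) by trained site staff". It then says: "At Visit 3, subjects will be dosed three times in-office from the same kit by trained site staff". If a pregnancy is found, the early-termination text in 8.3.1 has the subject discontinued and the outcome of the pregnancy documented.

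**The concern.** The schedule is consistent across the protocol, so this is a design choice and not a contradiction. The difficulty is where the tests fall. By list order, the test precedes the vehicle instillation at Visit 1 and the first dose at Visit 3. The one dosing day without a test is the day on which randomized treatment starts, so the eligibility review at Visit 2 has no current result to look at.

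A site that follows the plan exactly could randomize a subject whose pregnancy a Visit 2 test would have shown, give her four doses, test her the next day and then discontinue her. A Day 2 test shows little that a Day 1 test would not, but it comes after exposure has begun. With a Day 1 test before randomization she would be a screen failure with no randomized exposure. Under SAP 8.1 a randomized Main Cohort subject stays in the ITT population, so if she were discontinued before the Day 2 CAE she would also contribute no primary-endpoint data. At the numbers expected, that has no practical effect on the analysis.

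**Working it through.** **Inputs from the documents**

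- Visit 1: Day -14, window -16/+2 days (Protocol 8.3.1; SAP 4.1, Table 1).
- No Day 0; Day 1 is the day of randomization (SAP 4.1).
- Randomized doses: four at Visit 2, three at Visit 3 (Protocol 7.1.4).
- Planned size: 20 in the Initial Cohort and about 300 in the Main Cohort (Protocol Section 4 and 5.1).

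**Check of the calendar against the plan's own figure**

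The synopsis puts participation at about 16-32 days. Counting inclusively to Day 2, a Visit 1 on Day -14 gives 14 + 2 = 16 days and one on Day -30 gives 30 + 2 = 32 days, so the figure is reproduced. The late edge of the window, Day -12, gives 14 days, which falls a little outside the approximate range.

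**Age of the Visit 1 test at the first randomized dose**

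- Earliest: -14 - 16 = Day -30, which is 30 days before Day 1.
- Nominal: Day -14, which is 14 days before.
- Latest: -14 + 2 = Day -12, which is 12 days before.

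**Doses before the next scheduled test**

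4 / (4 + 3) = 4/7, or 57%. That the Visit 3 test precedes that visit's dosing rests on list order, but at least four doses precede it in any case.

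**Expected number of subjects**

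The documents give neither the share of subjects of childbearing potential nor a pregnancy rate. Assumed ranges: share 15-30%, rate 0.3-1% per month.

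Expected cases = N × share × monthly rate × gap/30

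| N | Gap (days) | Low | High |
|---|---|---|---|
| 320 | 14 | 320 × 0.15 × 0.003 × 14/30 = 0.067 | 320 × 0.30 × 0.01 × 14/30 = 0.448 |
| 300 | 14 | 300 × 0.15 × 0.003 × 14/30 = 0.063 | 300 × 0.30 × 0.01 × 14/30 = 0.42 |
| 300 | 12 | 300 × 0.15 × 0.003 × 12/30 = 0.054 | 300 × 0.30 × 0.01 × 12/30 = 0.36 |
| 300 | 30 | 300 × 0.15 × 0.003 × 30/30 = 0.135 | 300 × 0.30 × 0.01 × 30/30 = 0.90 |

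With 1:1 allocation, about half would be assigned reproxalap: 0.03 to 0.21 at the nominal gap, and 0.90 / 2 = 0.45 at the extreme.

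**With a negative test required at Visit 2 before randomization**

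The result is 0 days old at the first randomized dose, and 0 of 7 doses precede a current result.

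**The case against.** The strongest reply is that the yield is very low. At the nominal gap the expected number on reproxalap is 0.03 to 0.21 in the whole Main Cohort, and the 0.90 figure needs every subject screened at Day -30 with both assumptions at their high end. Nor does the formula credit the medical update and eligibility review at Visit 2, where a subject who suspects a pregnancy may say so. All of this stands. For given inputs the figures are on the high side as a measure of what the test adds, and 0.90 is a bound.

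It can also be said that the readable documents show no reproductive hazard from a few topical doses, since risk information is left to the Investigator's Brochure. That limits any claim about harm. It does not remove the point, because pregnancy is the sponsor's own exclusion criterion and the sponsor already chose to check it by urine test. Self-report and contraception cannot detect a pregnancy that the subject has not recognized.

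Moving the Visit 3 test would give up the exit test. This too is fair, and the sponsor can keep both at the price of one more test.

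Finally, the Appendix 1 schedule is not shown in the public copy and SAP Table 2 is unreadable. However, criterion 13 names the test visits, and every item in the 8.3.1 Visit 2 list up to randomization is legible, so a hidden Visit 2 test is unlikely.

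**Conclusion.** The concern holds. As written, the pregnancy exclusion is checked at randomization against a result 12 to 30 days old, and the next test follows four of the seven randomized doses. These figures rest only on the visit window, the absence of a Day 0 and the dosing schedule.

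The expected number affected is well below one at the nominal gap: 0.06 to 0.42 in the Main Cohort. It spans 0.05 to 0.90 over the whole window, under the assumed share and rate. A Visit 2 test would reduce such exposure but not eliminate it, because a very recent conception also tests negative on Day 1. Nothing in alpha, power or sample size changes. The change is worth making because the exposure is avoidable and the remedy is cheap, not because many cases are expected.

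**What to change.** Require a negative urine pregnancy test at Visit 2, before the randomization step, for subjects of childbearing potential. Amend criterion 13 in the synopsis and in 5.4, the Section 4 table, the Visit 2 and Visit 3 lists in 8.3.1, and Appendix 1. The simplest form moves the Visit 3 test one day earlier. Keep the early-termination test, and keep a Day 2 exit test if the sponsor wants one.

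The cost is wording in the protocol and source documents, and in the consent form if it lists tests by visit, with sponsor and IRB review. Scheduled tests for a completing subject stay at two if the Day 2 test is given up, or rise to three if it is kept. SAP 5.2 reports that the Initial Cohort has already been unmasked, so the change could reach only Main Cohort subjects not yet randomized. The documents do not say how many of these remain.
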